**BACKGROUND:**

Hypothermia is a core temperature less than 36°C in surgical patients, affecting up to sixty-four percent. All surgical patients are at increased risk as intrinsic thermoregulation is impaired by anesthetics' effects, increasing the core temperature threshold from 0.2°C to 4°C; this delays normal compensatory mechanisms. This effect is compounded by the cold surgical environment, IV fluids, and airway gases. Hypothermia is known to have several deleterious complications.

Surgical site infections occur more frequently, as there is increased vasoconstriction near surgical wounds, which decreases oxygen and nutrient delivery. Immune function also is impaired from raised interleukin-6 levels and damaged neutrophils. Coagulopathies are more prevalent because of impaired clotting cascade enzymes and platelet function as well as increased fibrinolysis. As a result, greater blood loss and subsequent transfusions are observed, up to 16% and 22%, respectively. Colder patients experience increased cardiac-related events, as norepinephrine levels can be 7-fold, precipitating hypertension, angina, and myocardial ischemia. In addition, drug metabolism is decreased, prolonging medication effects and increasing potency. Post-anesthesia shivering is more observed in hypothermic patients, which can increase oxygen consumption, with estimates 110% or greater. Pressure ulcer formation and greater postoperative pain are further described. These events significantly impact surgical patients as there is increased time to extubation, post-anesthesia recovery, hospitalization, and mortality.

Heat is lost through radiation, convection, conduction, and evaporation, with radiation and convection being the most significant sources. Patients try to maintain

normothermia, defined by Hooper et al as a core temperature between 36°C and 38°C. This mechanism, however, is disrupted through three phases during surgery. Post-induction is the first phase, with anesthetics inducing vasodilation, even in response to cold-stressors; this abruptly shifts core heat peripherally, as there is a decrease of 1-1.5°C within the first hour. The second phase occurs over the next 1-2 hours and is associated with a slow, linear heat loss as the heat deficit exceeds heat production. Phase III occurs after three hours of induction and is associated with a plateau state as peripheral vasoconstriction is triggered in an attempt to reestablish thermoregulation.

The standards of practice for the American Society of Anesthesiologists and the American Association of Nurse Anesthetists recommend that patient temperature should be monitored and maintained when significant changes are anticipated or suspected. This is also supported through the clinical practice guideline by the American Society of PeriAnesthesia Nurses, which states “frequent intraoperative temperature monitoring should be considered in all cases”(p.353) as well as proper assessment for hypothermia. The Centers for Medicare and Medicaid Services (CMS) initiated the Surgical Care Improvement Project-Infection-10 (SCIP-Inf-10) in 2009 as means for maintaining normothermia in surgical patients undergoing general or neuraxial anesthesia for greater than one hour, which was required for hospitals participating in CMS. SCIP-Inf-10 applied reimbursement costs the following two ways: 1) maintaining a patient’s temperature at least 36°C within 30 minutes before or 15 minutes after anesthesia’s end time or 2) attempting to maintain patient normothermia by active warming methods. SCIP-Inf-10 was retired January 1, 2014 as an active measure for The Joint Commission and CMS. However, CMS in December 2014 as part of their “List of Measures under Consideration Table” included the normothermia outcome defined as the following to be addressed: “This measure

evaluates whether patients having surgical procedures under general or neuraxial anesthesia of 60 minutes or more in duration are normothermic within 15 minutes of arrival in PACU.”(np)

Achieving normothermia on arrival to the PACU is only a partial goal as deleterious effects can be potentiated intraoperative while seemingly corrected postoperative. Coagulation during surgery is dynamic as fluctuations according to patient temperature may or may not be noticed if the patient is normothermic in the PACU, even if they were hypothermic intraoperative. Sun et al included over 58,000 patients in their study to evaluate temperature patterns perioperative, demonstrating approximately 50% and 20% of patients having temperatures less than 36°C and 35.5°C for over an hour, respectively. Furthermore, 20% of these patients had temperatures less than 36°C for greater than two hours.

Several interventions are commonly utilized to manage patients’ temperatures intraoperative, such as blankets, circulating fluid mattresses, forced air warming, IV fluid warmers, and heated breathing circuits. The most used heating intervention is forced air warming as it is relatively inexpensive and increasing ambient temperature isn’t usually an option as the surgical staff can get too hot from their additional layers. Maintaining normothermia can be challenging utilizing only forced air warming in certain populations, such as patients undergoing spinal surgery. These patients are positioned prone and active warming is often delayed more than 30 minutes. Employing multiple active warming devices has been suggested in several studies and may be a viable option to prevent hypothermia from developing.

Less than 10% of heat loss occurs via the airway; although, this has been suggested as a possible location for warming patients. Several studies have incorporated heated humidification as a warming method, but the results are conflicting regarding its effectiveness.

Some suggest no effects are achieved, while others have demonstrated higher initial temperatures following induction as well as maintaining these temperatures during surgery. Heated humidifiers use active warming and are shown to be superior compared to heat-moisture exchangers (HMEs), which passively warm the airway. Several studies have observed temperature changes of 0.5°C or greater in patients provided active heat and humidification compared to patients given none or passive humidification. A temperature difference of 0.5°C has demonstrated clinical relevance, as patients have less intraoperative blood loss, fewer transfusions, decreased post-anesthesia recovery, and less shivering.

Most of the current literature regarding heated breathing circuits focuses on surgeries three hours or less, with small to medium patient populations, and healthier adults. This study will expand on the previous works by concentrating on surgeries greater than three hours and including less healthy adults. This will allow for evaluation of active heat and humidification in regards to patients experiencing Phase II and Phase III, as it is suggested that active heat and humidification would have an increased effect on temperature as surgery length progresses compared to patients receiving none or passive humidification. The purpose of this study is to compare core temperatures in adult patients having lower spinal surgery for at least three hours in duration using either a heated ventilator circuit (ANAPOD™ Heat and Humidification System; Westmed) or a standard ventilator circuit with a HME (Thermovent® 600; Portex). The ANAPOD™ Heat and Humidification System (Westmed) provides active heat and humidification during anesthesia by warming inspiratory gases for intubated patients. The HME connects between the endotracheal tube (ETT) and the standard ventilator circuit and is our hospital's standard practice for all spine surgery patients.

**SPECIFIC OUTCOMES AND HYPOTHESIS:**

The primary outcome of this study is to compare core body temperature four hours after induction in patients having lower spinal surgery, of at least three hours in duration and using either a heated ventilator circuit (treatment group) or a standard ventilator circuit with a HME (control group). For any patient surgery with a core temperature not reaching four hours post-induction, the final esophageal temperature will be used. We hypothesize that the treatment group will have higher statistically significant temperatures four hours after induction or using the last recorded esophageal temperature for surgeries not reaching that timeframe compared to the control group.

A secondary outcome will compare overall patient temperature trends between the two groups, perioperatively. We hypothesize that the treatment group will have higher statistically significant temperatures perioperatively 60 minutes post-induction compared to the control group. An additional secondary outcome will compare patient shivering between the two groups. We hypothesize that the treatment group will have less shivering compared to the control group.

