**MATERIALS AND METHODS:**

[figure not shown]
Following Institutional Review Board approval, a randomized, prospective study will be conducted on Saint Mary's Campus at Mayo Clinic Hospital in Rochester, MN. Study participants will be patients  $\geq 18$  years old (including possible pregnant women), with an ASA status of I-III, and the following surgery inclusive criteria: elective spinal surgery greater than three hours in duration, posterior approach, an operation site between lumbar one and sacral one, involving two or more levels with fusion and/or instrumentation and/or revisions, and encompassing any anticipated possibilities for these mentioned criteria prior to surgery. Exclusion criteria are the following: patients with a tracheostomy, preoperative body temperature

>38°C or <36°C on the day of surgery, active infection or erythema to the back, or white blood cell count greater than 10,500/mcL (Figure 1).

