Patients will be randomly assigned to either the treatment group or the control group prior to surgery. Patients in the treatment group will be given heated and humidified inspiratory gases prior to being positioned prone following induction. Induction will be defined for this study as intubation since this will be the first opportunity to place an esophageal stethoscope with a temperature sensor as is the usual practice at our hospital. Distal esophageal temperature is a measure of patient core temperature and has been demonstrated to not be affected by tracheal temperatures if placed correctly in the retrocardiac portion of the distal esophagus. The retrocardiac position is represented by maximal heart sounds or 38-42cm as measured from the central incisors in adults. Education with anesthesia providers, incorporating visual aids and descriptive explanations, for placing the esophageal temperature probe at this location will be provided by a team member associated with this study prior to study enrollment. Even with proper education, this may be a study limitation if the probe isn't placed at the retrocardiac portion of the esophagus; however, this limitation should be minimized with the planned educational approach. All patients will receive a forced air warming blanket to their lower extremities and upper back at 43°C (high) after draping as is the usual practice at our hospital (Figure 2). If any patient has a temperature of 36°C for at least 15 minutes, both forced air warming controller devices will be turned off but remain in place under the drapes, as is the recommended practice at our hospital. If a patient's temperature decreases below 36°C, both forced air warming devices would again be turned on high setting (43°C). The operating room temperature will initially be set to 21°C by a team member associated with this study each morning prior to enrolled surgeries. The operating room temperature will be maintained at 20-

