22°C, but may be adjusted beyond this range at the surgeon's discretion and/or subject's condition. The room temperature will be documented for all subsequent subjects every hour using an in-room digital display temperature device. It is important to standardize flow settings and tidal volumes as both may impact the amount of delivered heat to the patient, and it is recognized that these settings may be difficult to maintain during induction or patient positioning as higher volumes are generally given. The ventilator flow setting will be maintained at  $\leq 2$ L/min or adjusted to meet the patient's needs during anesthetic maintenance, with tidal volumes 6-8ml/kg following patient positioning and induction. Patient randomization will assist with reducing any other potential sources of variation that may occur, such as patient exposure time during positioning.

**FIGURE 1:** Describes patient selection process

Patient's temperature will be measured and recorded in the preoperative area at least once prior to entering the OR suite. Intraoperative, patient's temperature will be measured and recorded within ten minutes or the first stable temperature reading after induction to establish a baseline. To allow for patient repositioning, the next temperature will be recorded within 30 minutes of the baseline esophageal temperature and every 10 minutes thereafter for the first hour post-induction, followed subsequently every 30 minutes until the patient is repositioned supine. Following the surgery, the patient will be transferred to the PACU, where the temperature will be measured and recorded at least once within 15 minutes of arrival (Figure 2). Oral temperatures (or axillary temperatures if an oral temperature cannot be obtained) will be used in the preoperative area, PACU, and ICU while esophageal temperatures will be measured in the OR suite after induction.

[figure not shown]
Patients will be monitored in the PACU for shivering as this can be an indicator of hypothermia. Any patients transferred directly to ICU from surgery will have a temperature recorded within 15 minutes of arrival. Any patient transferred to ICU will not be monitored for shivering. All patients' electronic medical records will be monitored through their hospital discharge, up to 30 days post-surgery to record any postoperative complications.

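### The primary outcome pools four-hour readings with earlier last readings, so it does not by itself estimate a four-hour difference, and no planned contrast does

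*Combined protocol and SAP*

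**What the plan says.** The section on specific outcomes and hypothesis sets out to "compare core body temperature four hours after induction in patients having lower spinal surgery, of at least three hours in duration". Materials and Methods starts the clock: "Induction will be defined for this study as intubation". Entry requires "elective spinal surgery greater than three hours in duration", and the surgical criteria are judged on what is anticipated before the operation.

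For operations that stop short of four hours, the rule is: "For any patient surgery with a core temperature not reaching four hours post-induction, the final esophageal temperature will be used". The same fallback is written into the hypothesis, Table 1 and the primary analysis. The primary analysis is an ANCOVA in which pre-induction temperature is the only covariate named.

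After the first hour, readings are taken at intervals, "followed subsequently every 30 minutes until the patient is repositioned supine". The statistical section also plans a mixed linear model on all intraoperative esophageal readings. It names time as a within-subject effect and treatment group as a between-subject effect. No group-by-time interaction is named, and no difference at a stated time.

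On the time course, the Background reports a suggestion that "active heat and humidification would have an increased effect on temperature as surgery length progresses". It also says that "Phase III occurs after three hours of induction", and describes that phase as "associated with a plateau state as peripheral vasoconstriction is triggered".

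**The concern.** Entry duration and primary time point do not match. A correctly enrolled and treated patient whose operation ends before four hours after intubation contributes an earlier reading, and it counts in the ANCOVA exactly as a four-hour reading does. The estimated difference is therefore an average over reading times, weighted by how long the enrolled operations happen to last.

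This matters because the protocol itself gives timing a role. It offers evaluation into Phases II and III as what the study adds, and it cites a suggestion that the device effect increases as surgery goes on. If so, earlier readings carry a smaller effect and pull the estimate down. A positive result would then not be a four-hour difference. A null result would leave open how much was dilution, unless the serial readings are analysed to show it.

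**Working it through.** **Inputs from the documents.** Difference to detect 0.5°C, SD 0.6°C, two-sided alpha 0.05, power 90%, 32 per group analysed and 35 per group enrolled (Statistical Considerations/Analysis). The attrition allowance names surgery shorter than three hours. It says nothing about operations that end between three and four hours after intubation.

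**The plan's own figure.** The two-sample normal approximation gives 31 per group. By the exact t test, power is 89.8% at 31 per group and 90.7% at 32. So 32 is the smallest group size that reaches 90%, and the stated 64 in total is reproduced.

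**Inputs that must be assumed.** The documents give no distribution of operation length and no growth curve. I take:
- f, the share of analysed patients whose primary value is a last reading before four hours: 25%, 50% or 75%;
- t, the mean time of those readings after intubation: 3.25 or 3.5 h;
- a true difference of 0.5°C at four hours.

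**Formula.** Analysed difference = (1 − f) × 0.5 + f × effect(t). Loss = 1 − analysed difference / 0.5.

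Three shapes for the effect:
- *Flat after three hours:* effect(t) = 0.5.
- *Linear from intubation:* effect(t) = 0.125 × t, so 0.406°C at 3.25 h and 0.4375°C at 3.5 h.
- *Late-rising:* effect(t) = 0.2 + 0.3 × (t − 3), so 0.275°C at 3.25 h and 0.35°C at 3.5 h.

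Worked example (linear, f = 0.50, t = 3.5): 0.5 × 0.5 + 0.5 × 0.4375 = 0.469°C, and the loss is 1 − 0.469/0.5 = 6%.

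In each cell the first value is for t = 3.25 h and the second for t = 3.5 h.

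| Shape | f = 25% | f = 50% | f = 75% | Loss over the range |
|---|---|---|---|---|
| Flat after 3 h | 0.500 / 0.500 | 0.500 / 0.500 | 0.500 / 0.500 | 0% |
| Linear | 0.477 / 0.484 | 0.453 / 0.469 | 0.430 / 0.453 | 3–14% |
| Late-rising | 0.444 / 0.463 | 0.388 / 0.425 | 0.331 / 0.388 | 8–34% |

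**Power** (t test, 32 per group, no allowance for precision gained from the covariate): 90.7% if flat, 81–89% if linear, 58–86% if late-rising.

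The bottom of the late-rising row needs three things at once: three-quarters of patients on the fallback, a mean last reading at 3.25 h, and an effect that more than doubles in one hour. The documents support none of these, so I treat that row as a stress case.

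**What the mixed model would give.** As written, with time and group effects only, it yields one group difference averaged over all readings. It uses real reading times and carries nothing forward, so the needed data are collected. What is missing is the term that lets the difference vary with time, and a contrast at a named time.

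**The case against.** The strongest reply is that nothing is hidden. The fallback stands in the outcome, the hypothesis, Table 1 and the analysis, so a reader who infers an undisclosed substitution or an internal contradiction would be wrong. That stands. It is a design choice, and what remains is how the result is interpreted.

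Three further objections also stand:
- **Two clocks.** Entry counts operation length, while the endpoint counts from intubation, which precedes prone positioning and draping. A reader might infer that every operation of three to four hours supplies a substituted value. Some will still have a four-hour reading, which lowers the share affected.
- **Plateau.** The Background describes core temperature levelling off after about three hours, so the loss may be zero. The plateau concerns temperature, not the difference between arms, and the Background separately suggests a growing effect. The documents do not settle which holds.
- **No universal landmark.** One might infer that every patient has a reading at exactly 180 minutes. Entry rests on anticipated duration, surgery under three hours is foreseen, and the schedule runs from a baseline of variable timing.

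A reader might also infer that last readings are taken with drapes and forced air already removed. The plan does not say when these come off and requires no reading at that moment, so this is conjecture.

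The objection that the mixed model already covers the matter stands only in part: it uses the right data, but no common-time difference is specified.

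**Conclusion.** The concern holds in a limited form. The primary analysis validly compares the randomised groups on temperature at four hours or at the last reading if earlier. It does not estimate the difference at four hours, and no planned contrast does. The documents do not support a stronger reading, namely that the comparison is biased between arms or that dilution is established.

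The size cannot be computed from the documents. Under the assumed shares and reading times it is 0% if the difference is flat after three hours and about 3–14% of 0.5°C if it grows linearly from intubation. It exceeds that only if growth is concentrated after three hours. This is worth a cheap change to the analysis plan. It does not call for a new primary endpoint or a larger sample.

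**What to change.** Keep the primary rule and the sample size. Before the data are analysed:

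1. In the planned mixed model, pre-specify a group-by-time interaction using actual time from intubation. Report the group difference with its confidence interval at 180 and 240 minutes, carrying no readings forward, as supportive analyses.
2. Report by arm how many primary values are last readings taken before four hours, and when they were taken.
3. Describe the primary result as temperature at four hours or at the last reading if earlier. Make a specific four-hour statement only with the 240-minute contrast shown beside it.

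The cost is a few lines of analysis plan and some extra output from data already collected, with no added patients or measurements. The downside is that the 240-minute contrast relies on a missing-at-random assumption for operations that have already ended. It is also less precise, and it could differ from the primary result. For these reasons it should stay supportive and not replace the primary analysis.

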**MATERIALS AND METHODS:**

[figure not shown]
Following Institutional Review Board approval, a randomized, prospective study will be conducted on Saint Mary's Campus at Mayo Clinic Hospital in Rochester, MN. Study participants will be patients  $\geq 18$  years old (including possible pregnant women), with an ASA status of I-III, and the following surgery inclusive criteria: elective spinal surgery greater than three hours in duration, posterior approach, an operation site between lumbar one and sacral one, involving two or more levels with fusion and/or instrumentation and/or revisions, and encompassing any anticipated possibilities for these mentioned criteria prior to surgery. Exclusion criteria are the following: patients with a tracheostomy, preoperative body temperature

>38°C or <36°C on the day of surgery, active infection or erythema to the back, or white blood cell count greater than 10,500/mcL (Figure 1).

Patients will be randomly assigned to either the treatment group or the control group prior to surgery. Patients in the treatment group will be given heated and humidified inspiratory gases prior to being positioned prone following induction. Induction will be defined for this study as intubation since this will be the first opportunity to place an esophageal stethoscope with a temperature sensor as is the usual practice at our hospital. Distal esophageal temperature is a measure of patient core temperature and has been demonstrated to not be affected by tracheal temperatures if placed correctly in the retrocardiac portion of the distal esophagus. The retrocardiac position is represented by maximal heart sounds or 38-42cm as measured from the central incisors in adults. Education with anesthesia providers, incorporating visual aids and descriptive explanations, for placing the esophageal temperature probe at this location will be provided by a team member associated with this study prior to study enrollment. Even with proper education, this may be a study limitation if the probe isn't placed at the retrocardiac portion of the esophagus; however, this limitation should be minimized with the planned educational approach. All patients will receive a forced air warming blanket to their lower extremities and upper back at 43°C (high) after draping as is the usual practice at our hospital (Figure 2). If any patient has a temperature of 36°C for at least 15 minutes, both forced air warming controller devices will be turned off but remain in place under the drapes, as is the recommended practice at our hospital. If a patient's temperature decreases below 36°C, both forced air warming devices would again be turned on high setting (43°C). The operating room temperature will initially be set to 21°C by a team member associated with this study each morning prior to enrolled surgeries. The operating room temperature will be maintained at 20-

22°C, but may be adjusted beyond this range at the surgeon's discretion and/or subject's condition. The room temperature will be documented for all subsequent subjects every hour using an in-room digital display temperature device. It is important to standardize flow settings and tidal volumes as both may impact the amount of delivered heat to the patient, and it is recognized that these settings may be difficult to maintain during induction or patient positioning as higher volumes are generally given. The ventilator flow setting will be maintained at  $\leq 2$ L/min or adjusted to meet the patient's needs during anesthetic maintenance, with tidal volumes 6-8ml/kg following patient positioning and induction. Patient randomization will assist with reducing any other potential sources of variation that may occur, such as patient exposure time during positioning.

**FIGURE 1:** Describes patient selection process

Patient's temperature will be measured and recorded in the preoperative area at least once prior to entering the OR suite. Intraoperative, patient's temperature will be measured and recorded within ten minutes or the first stable temperature reading after induction to establish a baseline. To allow for patient repositioning, the next temperature will be recorded within 30 minutes of the baseline esophageal temperature and every 10 minutes thereafter for the first hour post-induction, followed subsequently every 30 minutes until the patient is repositioned supine. Following the surgery, the patient will be transferred to the PACU, where the temperature will be measured and recorded at least once within 15 minutes of arrival (Figure 2). Oral temperatures (or axillary temperatures if an oral temperature cannot be obtained) will be used in the preoperative area, PACU, and ICU while esophageal temperatures will be measured in the OR suite after induction.

[figure not shown]
Patients will be monitored in the PACU for shivering as this can be an indicator of hypothermia. Any patients transferred directly to ICU from surgery will have a temperature recorded within 15 minutes of arrival. Any patient transferred to ICU will not be monitored for shivering. All patients' electronic medical records will be monitored through their hospital discharge, up to 30 days post-surgery to record any postoperative complications.

Shivering in the PACU will be assessed at least every 30 minutes for a maximum of two hours using the Bedside Shivering Assessment Scale (BSAS) described by Badjatia et al (Table 1). This is a 4-point scale and rates shivering as the following: absent, mild, moderate, or severe (Table 2). Absent means "no shivering noted on palpation of the masseter, neck, or chest wall."67(p3243) Mild means "shivering localized to the neck and/or thorax only."67(p3243) Moderate means "shivering involves gross movement of the upper extremities (in addition to

neck and thorax),”(p3243) and severe means “shivering involves gross movements of the trunk and upper and lower extremities.”67(p3243) The BSAS demonstrated reliability among multiple users and was tested for validity using indirect calorimetry (IDC) at rest. IDC is often performed at rest and provides reliable, precise measurements of resting energy expenditure, which contribute largely to the total daily energy expenditure. Nurses in the PACU will be educated to use this scale by a team member associated with this study.

FIGURE 2: Describes perioperative timeline and outcome measurement events

11

**TABLE 1:** Describes study outcomes

OUTCOME	LOCATION	DESCRIPTION
Primary: Post-induction temperature	Intraoperative	Patient core temperature four hours post-induction or using the last recorded esophageal temperature for surgeries not reaching that timeframe compared to initial baseline esophageal temperature
Secondary Perioperative temperature	Intraoperative, postoperative	Patient temperature trends intraoperative to postoperative.
Shivering	Postoperative	Presence of shivering among patients in the PACU as described by Bajjatia et al.  Assessed every 30 minutes for a maximum of two hours.

**TABLE 2:** Describes Bedside Shivering Assessment Scale developed by Bajjatia et al.

Score	Definition
0	None: no shivering noted on palpation of the masseter, neck, or chest wall
1	Mild: shivering localized to the neck and/or thorax only
2	Moderate: shivering involves gross movement of the upper extremities (in addition to the neck and thorax)
3	Severe: shivering involves gross movements of the trunk and upper and lower extremities

The ANAPOD™ Heat and Humidification System (Westmed) controller will be turned on prior to connecting the ventilator circuit to the ETT and will be set to 45°C with an acceptable fluctuation between 44-45.6°C. The temperature setting will be monitored and recorded every 30 minutes until extubation. This will be monitored by the anesthesia provider and documented in the patient's electronic medical record. The delivered temperature is expected to be 4-5°C less

than the administered temperature, which will provide airway gases at 40-41°C to patients in the treatment group. If the patient's temperature is >37.4°C for at least 15 minutes using only the ANAPOD™ Heat and Humidification System (Westmed), then the controller unit would be turned off until the patient's temperature is <37°C, at which point the controller's temperature setting would follow the previous outlined parameters. The ventilator circuit associated with the ANAPOD™ Heat and Humidification System (Westmed) is comprised of a heated wick and has a water trap on the expiratory limb to prevent humidity impacting the ventilator. A 0.5 micron hydrophobic filter (Smiths-Medical) will be placed at the patient-end of the gas sample line to prevent humidity impacting the gas analyzer. The ANAPOD™ Heat and Humidification System (Westmed) is a FDA approved device for all patient populations and uses sterile water for adding humidification to the ventilator circuit. This device has been approved by the Anesthesiology Equipment Committee and Anesthesia Biomed Department for this study. A team member associated with this study will provide education to anesthesia providers for using this equipment.

An investigator associated with this study will meet patients in the Preoperative Evaluation Clinic located at Gonda or the AM admit areas (on Alfred-1 or EPACU) located at St. Mary's campus. The investigator will review the consent form with patients meeting the study's eligibility requirements and enroll patients who are willing to provide written, informed consent. Patients will be randomized to the study after consent and enrollment as described in the section below.

